6.6 Secondary Endpoints

6.6.1 Binary Responses

The same test as described in the previous section 6.5, will be applied to each of the binary responses (no sensitivity analyses will be performed).

Note that all these analyses will be repeated for ITT, mITT and PP population.

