Phase 2 Study XSMP-202 compared the safety and efficacy of oral glucose tablets to mini-doses (0.15 and 0.3 mg) of Xeris Glucagon RTU SC administered to T1D subjects as treatment/prevention of mild to moderate hypoglycemia. A total of 20 subjects between the ages of 18 and 64 years were randomized in this 3-week, 2-period cross-over study with a 3-week follow-up period during which subjects had free choice of using either Glucagon RTU or glucose tablets to treat/prevent hypoglycemia. Glucagon RTU successfully treated mild-to-moderate hypoglycemia and may be a useful alternative to treatment with oral carbohydrate. All treatments were well tolerated, no SAEs were observed and AEs were generally of mild severity and consisted primarily of pain or tingling at the injection site. Observations of edema and erythema were generally mild and transient. Nausea occurred only at the higher dose of 0.3 mg, in one-third of the subjects.

Phase 3 Study XSGP-301 was a non-inferiority, randomized, single-blind, 2-way crossover comparative efficacy and safety trial in adult subjects with T1D. The study demonstrated that G-Pen 1 mg SC was comparable to Lilly Glucagon via an intent-to-treat analysis. The study demonstrated that administration of G-Pen and Lilly Glucagon either increased plasma glucose ≥ 20 mg/dL at 30 minutes post-injection or resulted in a plasma glucose > 70 mg/dL within 30

minutes post-injection. Symptomatic relief of hypoglycemia after glucagon injections was similar for G—Pen compared with Lilly Glucagon, based on the trends observed across average hypoglycemia symptom questionnaire scores. Symptom scores did not differ significantly between treatment groups for average autonomic, neuroglycopenic, or overall symptoms. As expected for both Glucagon RTU and Lilly glucagon, as plasma glucose levels increased, mean hypoglycemia symptom scores decreased with peak symptom relief occurring approximately 30 minutes post injection. G-Pen injections to the abdomen around the umbilicus demonstrated faster absorption when compared to injections to the outer arm and outer leg. Both G-Pen and Lilly Glucagon were generally safe and well tolerated and safety findings were generally similar between the two treatment groups. The most common treatment-emergent adverse event (TEAE) was nausea, which was reported more frequently for subjects after G-Pen treatment compared with Lilly Glucagon.

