5.3.6.2.4 Binary Responses

For secondary response endpoints the following parameters will be defined:

Positive Symptomatic Response

Positive Symptomatic Response is defined as relief of neuroglycopenic symptoms (ANS) within 30 minutes from a decision to dose.

Positive Treatment Response

Positive Treatment Response is defined as exhibiting either a positive plasma glucose response (PGR) or a positive symptomatic response.

The following secondary response endpoints will be assessed.

1. Rate of failing to achieve a Positive Plasma Glucose Response 1 (PGR1).
2. Rate of failing to achieve a Positive Plasma Glucose Response 2 (PGR2).
3. Rate of failing to achieve a Positive Symptomatic Response.
4. Rate of failing to achieve a Positive Treatment Response.

For these secondary endpoints, analysis will be the same that for primary endpoint (PGR) described above in [section 5.3.6.1](#). Actual time will be used for calculations.

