6.5 Analysis of Primary Endpoint

The primary endpoint analysis will be based on the risk difference in rates of failing to achieve Positive Plasma Glucose Response (PGR) of G-Pen versus GlucaGen Hypokit and a 95% CI will be calculated. Non-inferiority will be declared if the upper limit of the 95% confidence interval for the difference in failure rates is $\leq 5\%$; where the absolute failure rate of G-Pen treatment is $\leq 5\%$. This analysis will be repeated for ITT, mITT and PP populations.

Subjects who are missing the primary endpoint for a study treatment will be considered as having a failure in the primary analysis for that treatment administration. This imputation will be conducted for both the ITT and the mITT populations. If a subject received the same two treatment administrations for both periods (Period 1 and Period 2), only the visit with the planned treatment received will be included in the primary analysis and the subject will be considered a failure in the primary analysis for the for unreceived treatment administration (ITT, mITT). For all other analyses, data will be included for only the planned treatment received in those analyses.

A sensitivity analysis will be performed for where all missing data will be considered a success and the same analysis as above completed.

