6.6.2 Pharmacodynamics Analyses

All PD parameters will be presented descriptively.

A mixed model with treatment, period and treatment*period as fixed factors and subject as a random factor will be applied to compare the least square mean differences. Log transformation will be applied if skewness is observed. Unstructured covariance matrix will be used for the covariance matrix unless the model failed. In such case, structured covariance matrix will be selected based on the one given the smallest AIC (Akaike Information).

P-value for the difference test and 95% confidence for non-inferior test will be reported.

Additionally, mean glucose curve from 0 to 180 minutes post receiving glucagon will be presented graphically for each treatment. For this group of figures, the protocol defined time will be used. The mean glucose curve during hypoglycemia induction time will also be presented for each treatment. Since there is no protocol time for hypoglycemia induction stage, the mean glucose will be summarized for every 5 minutes based on the glucagon injection time.

This will be conducted based on the mITT population only.

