6.6.4 Time-to-Event Analyses

All the Time-to-Event Efficacy parameters will be presented descriptively.

A survival analysis will be conducted for comparing the difference between treatments.

Survival curves will be provided to compare both treatments graphically. Two-sided log-rank p-value for the difference will be reported.

This analysis will be repeated for ITT, mITT and PP population.

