14.2.2.3.1	Non-inferiority Analysis of Time (min) to Symptom Relief (Neuroglycopenic, Autonomic and Total) After Decision to Dose by Population and by Treatment (All Enrolled Patients)
14.2.2.3.2	Non-inferiority Analysis of Time (min) to Complete Resolution (Neuroglycopenic, Autonomic and Total) After Decision to Dose by Population and by Treatment (All Enrolled Patients)

Tables	
Number	Title
14.2.2.3.3	Non-inferiority Analysis of Time (min) to Resolution of the Overall Feeling of Hypoglycemia After Decision to Dose by Population and by Treatment (All Enrolled Patients)
14.2.2.3.4	Non-inferiority Analysis of Time (min) to the Minimal Post Baseline Score After Decision to Dose by Population and by Treatment (All Enrolled Patients)
14.2.2.4	Non-inferiority Analysis of Glucagon Preparation Time (min) by Population and by Treatment (All Enrolled Patients)
14.2.2.5.1	Non-inferiority Analysis of Study Drug Assignment Questionnaire by Treatment (Per-Protocol Population)
14.2.2.5.2	Non-inferiority Analysis of Mean Visual Analog Scale (VAS) (Intent-to-Treat Population)
14.3.1.1	Overview of Adverse Events (Safety Population)
14.3.1.2.1	Summary of Treatment-Emergent Adverse Events by System Organ Class, Preferred Term and by Treatment (Safety Population)
14.3.1.2.2	Summary of Treatment-Emergent Adverse Events by System Organ Class, Preferred Term, Period and by Treatment Sequence (Safety Population)
14.3.1.3.1	Summary of Treatment-Emergent Adverse Events by System Organ Class, Preferred Term, Severity and by Treatment (Safety Population)
14.3.1.3.2	Summary of Treatment-Emergent Adverse Events by System Organ Class, Preferred Term, Severity, Period and by Treatment Sequence (Safety Population)
14.3.1.4.1	Summary of Treatment-Emergent Adverse Events by System Organ Class, Preferred Term, Relationship to Study Drug and by Treatment (Safety Population)
14.3.1.4.2	Summary of Treatment-Emergent Adverse Events by System Organ Class, Preferred Term, Relationship, Period to Study Drug and by Treatment Sequence (Safety Population)
14.3.1.5.1	Summary of Serious Adverse Events Leading to Study Discontinuation by System Organ Class, Preferred Term and by Treatment (Safety Population)
14.3.1.5.2	Summary of Serious Adverse Events Leading to Study Discontinuation by System Organ Class, Preferred Term, Period and by Treatment Sequence (Safety Population)

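### SAP 6.6.1 carries the primary 5% margin and 5% failure cap to symptomatic response without justification, and 12 non-binary tables are titled as non-inferiority analyses with no margin

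*SAP*

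**What the plan says.** **Binary secondary endpoints.** SAP 6.6.1 states: "The same test as described in the previous section 6.5, will be applied to each of the binary responses". The test in 6.5 has two conditions. The first begins "Non-inferiority will be declared if the upper limit of the 95% confidence interval for the difference in failure rates is" and sets 5%. The second is attached to it, "where the absolute failure rate of G-Pen treatment is", and also sets 5%. SAP 5.3.6.2.4 covers the same four endpoints (PGR1, PGR2, symptomatic response, treatment response) and says "For these secondary endpoints, analysis will be the same that for primary endpoint (PGR) described above", but the section it names is 5.3.6.1. That section specifies a risk difference in failure rates with 95% CIs. It contains no margin and no cap.

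**Symptomatic response.** SAP 5.3.6.2.4 defines it as neuroglycopenic relief within 30 minutes, with the clock starting at the decision to dose. SAP 5.3.6.2.3 defines relief as an average score no more than one unit above the euglycemic baseline and limits evaluability to subjects with a baseline score of at least 2.

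**Non-binary endpoints.** For the PD parameters, SAP 6.6.2 says "P-value for the difference test and 95% confidence for non-inferior test will be reported". For the time endpoints, SAP 6.6.4 says "Two-sided log-rank p-value for the difference will be reported". SAP 5.3.6.3.7.3 compares mean VAS with a mixed model, and SAP 6.6.5 tests the treatment-guess questionnaire against 50%. Appendix 1 gives the corresponding tables titles such as "Non-inferiority Analysis of Glucagon Preparation Time (min) by Population and by Treatment (All Enrolled Patients". Neither document states a margin for any of these endpoints.

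**The concern.** The 5% limits fit an endpoint with success expected near 100%, which is what SAP 4.2 expects of the glucose response. No such expectation is stated for symptom relief, and the symptom window also has to absorb drug preparation time. If symptom failures are not rare, the absolute cap decides the result whatever the comparator does. G-Pen could then be denied non-inferiority on symptoms while performing as well as GlucaGen Hypokit or better.

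For the 12 non-binary tables the risk runs the other way. Without a margin, non-inferiority is undefined. A non-significant log-rank p-value under a non-inferiority title invites the reader to take absence of a detected difference as evidence of non-inferiority. Where a confidence interval is produced, the limit to compare it with would have to be chosen after the data are seen.

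**Working it through.** **Inputs.** n = 111 evaluable subjects (SAP 4.2). Limits of 5% and 5% (SAP 6.5). Unpaired risk-difference interval (SAP Appendix 2, PROC FREQ with riskdiff). The plan gives no power, margin or expected failure rate for any secondary endpoint, so there is no figure of its own to reproduce. The symptom-failure rates below are an assumed range.

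**Step 1: the cap.** 5/111 = 4.5% and 6/111 = 5.4%, so at most 5 G-Pen failures are allowed. The binomial probability of 5 or fewer failures in 111 is 0.976 at a true rate of 2%, 0.518 at 5%, 0.029 at 10% and 0.0004 at 15%.

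**Step 2: the confidence limit.** Upper limit = (a − b)/n + 1.96 × √[pₐ(1 − pₐ)/n + p_b(1 − p_b)/n], where a and b are the G-Pen and GlucaGen failures, pₐ = a/n and p_b = b/n. With equal failures, a = b = 4 gives 1.96 × √(2 × 0.036 × 0.964/111) = 4.9%, which passes. a = b = 5 gives 5.5%, which does not.

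**Step 3: both conditions together.** Equal true failure rates, treatments independent, summed over all pairs (a, b):

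| True failure rate, both drugs | Limit ≤ 5% | Cap met | Full rule met |
|---|---|---|---|
| 1% | 92% | >99% | 92% |
| 2% | 77% | 98% | 77% |
| 5% | 44% | 52% | 40% |
| 10% | 26% | 3% | 3% |

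A paired interval with within-subject correlation 0.3 gives 96%, 86%, 44% and 3% for the full rule, so the pattern does not depend on the interval.

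**Step 4: G-Pen truly better.** Assume 10% failure on G-Pen and 20% on GlucaGen. SE = √[(0.09 + 0.16)/111] = 0.0475. The limit is met when the observed difference is below about 0.05 − 1.96 × 0.0475 = −0.043. That is (0.10 − 0.043)/0.0475 = 1.2 SE above the true value of −0.10, or about 88%; the exact sum gives 89%. The cap is met in 3%, and so is the full rule.

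**Step 5: table count.** Appendix 1 has 17 tables titled as non-inferiority analyses. Five are binary (14.2.2.1.1 to 14.2.2.1.5: one primary, four secondary). The other 12 are:

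| Tables | Endpoint | Planned inference | Margin |
|---|---|---|---|
| 14.2.2.2.1–4 | Cmax, Tmax, AUC0-90, AUC0-180 | Mixed model, p-value and 95% CI | None |
| 14.2.2.2.5, 14.2.2.3.1–4, 14.2.2.4 | Six time endpoints | Two-sided log-rank p-value | None |
| 14.2.2.5.1 | Treatment-guess questionnaire | Binomial test against 50% | None |
| 14.2.2.5.2 | VAS | Mixed model; code gives a CI for the difference | None |

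4 + 6 + 1 + 1 = 12.

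**The case against.** A reader might infer that the rule cannot work for symptoms because failure above 5% is likely on both drugs. The documents do not support that. The statement in Protocol 6.4 about study XSGP-301, "peak symptom relief occurring approximately 30 minutes post injection", describes when mean scores reached their best, and a subject can come within one unit of baseline well before then. The same section reports that in XSGP-202 symptoms had fully resolved in every subject by 30 minutes after injection, a stricter outcome than relief. That study was open-label, compared two doses of the sponsor's own product and timed from injection, so it does not settle the rate here, but it points to rare failures. At 1% to 2% failure the rule is usually met.

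A second tempting reading is that all 12 tables rest on difference tests alone. The four PD tables and the VAS table already get a 95% CI; what they lack is a margin. The description fits the six time tables and the questionnaire.

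Three further defences have weight:

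- The same test in 6.6.1 may mean only the risk-difference calculation, as 5.3.6.1 and the Appendix 2 code heading suggest. The text does not say so, and the analysis in 6.5 includes the declaration rule.
- SAP 8 says table names may change. That makes correction easy but does not supply a margin.
- The problem does not extend to every binary secondary endpoint. Protocol 13.3 applies the same 5%/5% rule to a rise of at least 20 mg/dL, which is PGR2. Treatment response includes the primary response, so on the same records its failure rate cannot exceed the primary's.

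Finally, an over-strict cap cannot create a false non-inferiority claim.

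**Conclusion.** The point holds in two parts. First, the 5%/5% rule reaches symptomatic response without justification, and 6.6.1 and 5.3.6.2.4 do not agree on whether the decision rule applies. The rule is fragile rather than unworkable: for identical products the chance of meeting it falls from 92% at 1% failure to 3% at 10%, and the cap can override a favourable comparison (89% against 3% in the assumed 10% v 20% case). These figures assume that all 111 subjects are evaluable and that outcomes on the two treatments are independent. The true symptom-failure rate is unknown, and the baseline-score restriction may reduce the number evaluable.

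Second, 12 tables carry a non-inferiority title with no margin, so none can support a non-inferiority conclusion; for the guess questionnaire the term has no meaning. The primary inference is untouched. The issue is what the trial may say about its secondary endpoints, and it should be settled before database lock.

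**What to change.** 1. State in the SAP that non-inferiority is declared only for the primary endpoint.
2. In 6.6.1, report symptomatic response as the failure-rate difference with a 95% CI and no 5%/5% declaration. Align the wording with 5.3.6.1 so that 6.6.1 and 5.3.6.2.4 describe one analysis.
3. Retitle tables 14.2.2.2.1–5, 14.2.2.3.1–4, 14.2.2.4 and 14.2.2.5.1–2 as comparisons.
4. For the six time endpoints, add a between-treatment effect estimate with a 95% CI beside the log-rank p-value. The PD and VAS intervals can stay as planned.

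If the sponsor wants a non-inferiority statement for a particular secondary endpoint, the alternative is to pre-specify and justify a margin for it before database lock.

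The cost is SAP text, table titles and one added estimate per time endpoint. No data collection changes. The downside is that secondary non-inferiority statements are given up.

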6.6.2 Pharmacodynamics Analyses

All PD parameters will be presented descriptively.

A mixed model with treatment, period and treatment*period as fixed factors and subject as a random factor will be applied to compare the least square mean differences. Log transformation will be applied if skewness is observed. Unstructured covariance matrix will be used for the covariance matrix unless the model failed. In such case, structured covariance matrix will be selected based on the one given the smallest AIC (Akaike Information).

P-value for the difference test and 95% confidence for non-inferior test will be reported.

Additionally, mean glucose curve from 0 to 180 minutes post receiving glucagon will be presented graphically for each treatment. For this group of figures, the protocol defined time will be used. The mean glucose curve during hypoglycemia induction time will also be presented for each treatment. Since there is no protocol time for hypoglycemia induction stage, the mean glucose will be summarized for every 5 minutes based on the glucagon injection time.

This will be conducted based on the mITT population only.

6.6.3 Neuroglycopenic, Autonomic, and Total Symptom scores

The average Neuroglycopenic, Autonomic and Total Symptom scores (ANS, AAS, and ATS) will be summarized descriptively at each of the protocol defined time points for each treatment group. A LOCF imputation will be used for post-baseline assessments to 90 minutes inclusively. Additionally, this will also be presented graphically.

Analysis will be conducted for the mITT population only and will use time from decision to dose.

6.6.4 Time-to-Event Analyses

All the Time-to-Event Efficacy parameters will be presented descriptively.

A survival analysis will be conducted for comparing the difference between treatments.

Survival curves will be provided to compare both treatments graphically. Two-sided log-rank p-value for the difference will be reported.

This analysis will be repeated for ITT, mITT and PP population.

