13.4.1. Pharmacodynamic Analyses

The PD endpoints will be derived from the individual glucose profiles.

Pharmacodynamic characteristics, including: plasma glucose area under the concentration versus time curve (AUC), C_{max} , and t_{max} , time to achieve a ≥ 20.0 mg/dL (≥ 1.11 mmol/L) increase from glucose nadir, and time to reach ≥ 70.0 mg/dL (≥ 3.89 mmol/L), will be compared between the treatment groups from time of glucagon administration. Comparison between the treatment groups will be performed using a mixed model with treatment, period and sequence as terms.

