13.4.2. Hypoglycemia Symptoms

Symptom relief will be analyzed as aggregate scores for the four autonomic symptoms, four neuroglycopenic symptoms, and 8 total (autonomic and neuroglycopenic) symptoms (see [Appendix 1](#)).

For analysis, “relief” will be defined as a return to a score no more than one unit above baseline symptoms during the euglycemic baseline period.

The time to the minimal score post baseline will be described and compared between the treatment groups using a mixed model with treatment, period and sequence as terms. Similarly, the time to first reporting of “no” for the overall hypoglycemia question (“Do you currently feel hypoglycemic?”) will be described and compared between the groups.

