5.3.6.2.3 Time-to-Event Efficacy Endpoints

Symptom relief will be analyzed as aggregate scores for the four autonomic symptoms, four neuroglycopenic symptoms, and 8 total (autonomic and neuroglycopenic) symptoms.

Symptom relief of hypoglycemia is defined as a return to a score (ANS, AAS, and ATS) no more than one unit above euglycemic baseline (1 / 2). Only subjects with baseline score at least 2 or more (for ANS, AAS, or ATS) will be evaluable for this analysis.

Complete resolution of hypoglycemia symptoms is defined as all symptoms in the domain (ANS, AAS, or ATS) have a score of 1 after receiving glucagon.

The time to resolution of the overall feeling of hypoglycemia is defined as first reporting of “No” for the global hypoglycemia question. This will be calculated as the difference (in mins) between the actual time when the first “No” for “Overall Assessment of Hypoglycemia” is observed and the time to decision of glucagon dosing.

Glucagon Preparation Time is defined as time to administer study drug from a decision to dose.

The following timing parameters will be calculated for analysis:

1. Time to a Positive Plasma Glucose Response (PGR) from injection of study drug.
2. Glucagon Preparation Time.
3. Time to symptom relief of autonomic and neuroglycopenic symptoms of hypoglycemia from a decision to dose. That include:
 - time to symptom relief of neuroglycopenic symptoms (ANS) from a decision to dose;
 - time to symptom relief of autonomic symptoms (AAS) from a decision to dose;
 - time to symptom relief of autonomic and neuroglycopenic symptoms (ATS) from a decision to dose;
4. Time to complete resolution of autonomic and neuroglycopenic symptoms of hypoglycemia from a decision to dose. That include:
 - time to complete resolution of neuroglycopenic symptoms (ANS) from a decision to dose;
 - time to complete resolution of autonomic symptoms (AAS) from a decision to dose;
 - time to complete resolution of autonomic and neuroglycopenic symptoms (ATS) from a decision to dose;
5. Time to minimal score of autonomic and neuroglycopenic symptoms of hypoglycemia from a decision to dose. That includes:
 - time to minimal score of neuroglycopenic symptoms (ANS) from a decision to dose;

- time to minimal score of autonomic symptoms (AAS) from a decision to dose;
 - time to minimal score of autonomic and neuroglycopenic symptoms (ATS) from a decision to dose;

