6 STATISTICAL METHODS

6.1 General Considerations

The statistical analyses will be performed using SAS Version 9.4 (or higher). All tables, figures and listings will be produced in landscape format.

Data will be presented at each scheduled timepoint (nominal time), where applicable. However, time-related endpoints (time to event) will be summarized using actual time.

For actual time, two reference points will be used: (a) decision to dose and/or (b) injection of study drug, which are specified in the primary and secondary endpoint analyses.

The total number of subjects in the study group (N) under the stated population will be displayed in the header of summary tables.

All study data will be included in the study data listings. Listings will be displayed by subject in chronological order, if not stated otherwise.

For tabulated safety summaries, only the scheduled timepoints will be included in the summary tables. Unscheduled assessments will be listed and used for evaluation of worst post-baseline value in categorical assessments, where applicable.

Sample codes and calculations for the efficacy analysis are provided in Appendix 2: Code Fragments. Actual code or procedure usage can differ from these samples, based on the model and conditions that correspond to those pre-specified in the SAP. Additional analysis may be performed for the cases not specified in SAP and will be described in CSR.

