10 DEVIATIONS FROM PLANNED ANALYSIS

For timing parameters mixed model analysis was replaced by time-to-event analysis.

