APPENDIX 2: CODE FRAGMENTS

Risk difference test for binary response

```
Proc Freq data = <Data> order=data;  
    weight Count / ZEROS;  
    tables <Treatment>*<Response> / riskdiff;  
    output out = <Out> riskdiff;  
run;
```

Mixed model

```
ods output lsmeans(match_all) = <Out_LSmean>  
           Diffs(match_all) = <Out_Diffs>;  
Proc Mixed data=<Data>;  
    class <Treatment> <Period> <Subject>;  
    model <Value> = <Treatment> <Period> <Treatment>*<Period>;  
    random <Subject> / Type = un;  
    lsmeans <Treatment> / cl DIFF;  
run;
```

Time-to-Event

```
ods output means=<Out_Means> HomTests=<Out_Test>;  
proc lifetest data=<Data>;  
    time <Time>;  
    strata <Treatment>;  
run;
```

Study Drug Assignment

```
proc freq data=<Data>;  
    tables <Treatment>/ BINOMIAL (p=0.50) alpha=0.05;  
    output out=<Out> Binominal;  
    weight count;  
run;
```

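### The timing endpoints of this two-way crossover are compared with an unpaired log-rank test that ignores subject and period, so with positive within-subject correlation the p-value is too large

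*SAP*

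**What the plan says.** - **The test.** SAP 6.6.4 plans descriptive summaries, survival curves and one inferential result: "Two-sided log-rank p-value for the difference will be reported". It names no subject term, no period term and no treatment contrast with a confidence interval.
- **The code.** The time-to-event fragment in SAP Appendix 2 groups by "strata <Treatment>" and nothing else. Its TIME statement carries no censoring variable.
- **What the protocol had.** For pharmacodynamic parameters, including the times to reach the glucose thresholds, Protocol 13.4.1 says: "Comparison between the treatment groups will be performed using a mixed model with treatment, period and sequence as terms". Time to minimal symptom score is to be "compared between the treatment groups using a mixed model with treatment, period and sequence as terms" (Protocol 13.4.2). The protocol names no model for symptom relief, complete resolution or preparation time.
- **What changed.** SAP section 10 states: "For timing parameters mixed model analysis was replaced by time-to-event analysis". It gives no reason and no paired substitute.
- **What the SAP keeps elsewhere.** SAP 6.6.2 uses "A mixed model with treatment, period and treatment*period as fixed factors and subject as a random factor" for the pharmacodynamic parameters, and SAP 5.3.6.3.7.3 uses the same model for VAS discomfort.

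**The concern.** In a two-way crossover the treatment comparison is made within subjects. SAP 4.2 relies on this when it says that power gains from subjects acting as their own controls. A two-sample log-rank gives that gain away. Its variance is the one that would apply if the two treatment groups were different people.

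When a subject's two times are positively correlated, that variance is too large, the test statistic is too small and the p-value is too large on average. A period effect, if there is one, adds noise that the test does not remove. The result is loss of sensitivity on secondary endpoints 5 (time to positive glucose response), 8 (symptom relief and resolution) and 9 (overall feeling of hypoglycemia), and formally on 6 (preparation time).

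**Working it through.** The documents state no power, effect size, spread or correlation for the timing endpoints, so there is no planned figure to reproduce. The only input taken from them is 111 evaluable subjects (SAP 4.2). The rest is assumed: log-normal times, median about 15 minutes, log-SD 0.45, and within-subject correlation ρ of 0.3, 0.5 or 0.7.

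**Step 1: direction.** With equal variance σ² on each drug, the variance of a within-subject difference is 2σ²(1 − ρ). An unpaired test uses 2σ². To a first approximation the unpaired z is therefore the correct z times √(1 − ρ), and

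actual two-sided error = 2 × [1 − Φ(1.96 / √(1 − ρ))].

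| ρ | 1.96/√(1 − ρ) | Actual error | Correct p of 0.05 is reported as |
|---|---|---|---|
| 0 | 1.96 | 5.0% | 0.05 |
| 0.3 | 2.34 | 1.9% | 0.10 |
| 0.5 | 2.77 | 0.6% | 0.17 |
| 0.7 | 3.58 | 0.04% | 0.28 |

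**Step 2: refinement for the log-rank.** Simulation of correlated pairs (3,000 runs per cell) gave a ratio of subject-clustered to naive variance of 0.73 / 0.55 / 0.35 under no treatment effect. Putting these in place of 1 − ρ:
- 1.96/√0.73 = 2.29, error 2.2%
- 1.96/√0.55 = 2.64, error 0.8%
- 1.96/√0.35 = 3.31, error 0.09%

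The directly simulated error was 2.3–2.6% / 0.8–0.9% / 0.1% or less over log-SD 0.35 to 0.60, in line with this.

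**Step 3: power for a 12% slowing** (111 pairs, log-SD 0.45). The comparator is a Cox model with treatment, period and subject-clustered variance. Its own error was 5.0–6.3%, so its power is taken at the cut-off that gives 5%.

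| ρ | Unpaired log-rank | Clustered Cox |
|---|---|---|
| 0.3 | 39% | 51% |
| 0.5 | 37% | 61% |
| 0.7 | 34% | 80% |

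**Step 4: a second simulation with other settings** (median 14 minutes, log-SD 0.4, times rounded up to the 5-minute sampling grid). Unpaired error was 2.5 / 1.0 / 0.2%. Power for a 12% slowing was 49 / 47 / 47% unpaired, 62 / 72 / 88% for a clustered log-rank and 67 / 80 / 92% for a period-adjusted paired comparison of log times. At correlation 0, unpaired and clustered power were 51% and 52%, so nothing is lost there.

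**Step 5: does the missing censoring variable change the test?** Assume correlation 0.5 and non-event rates of 20% on one drug and 5% on the other.

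| Non-events placed at | Mean z with flag | Mean z without flag |
|---|---|---|
| 180 min | −2.87 | −2.87 |
| 90 min | −2.84 | −2.84 |
| 30 min | −2.62 | −2.08 |
| 15 min | −0.98 | +0.57 |

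The flag matters to the test only when follow-up is cut while others are still having events.

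**The case against.** **The code is only a sample.** SAP 6.1 says: "Actual code or procedure usage can differ from these samples, based on the model and conditions that correspond to those pre-specified in the SAP". That permits variation within the pre-specified model, but 6.6.4 pre-specifies no paired or period-adjusted one. The objection fails for pairing. It does carry weight for censoring, because SAP 4.1 already provides for censoring after an intervention, so final code may include a flag.

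**Period is in the output.** Appendix 1 plans the survival curves by period and by treatment, and within one period the two treatment groups are different subjects. This is a fair point about the display. The corresponding test tables are titled by population and treatment only, so period does not enter the p-value.

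**The effect may be small.** A 12% slowing of an assumed 15-minute median is 0.12 × 15 = 1.8 minutes, less than the 5-minute sampling interval. No passage calls such a difference important, no success rule rests on these endpoints, and the replacement of the mixed model is disclosed. All of this stands, and it limits the weight of the point without making the test correct.

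**Stronger readings that the documents do not support.**
- A reader might infer that the missing censoring flag invalidates the comparison. The SAP calls a subject who answers yes throughout very rare, the protocol advises against intervention before 90 minutes, and Step 5 shows no change in mean z when non-events fall last.
- A reader might infer from the Appendix 1 titles, which call these tables non-inferiority analyses, that a large p-value will be used to claim similarity. SAP 6.6.4 plans a p-value for a difference, no margin for time is stated, and SAP section 8 lets table names change.

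**Conclusion.** The point holds. As written, the inferential comparison for the timing endpoints ignores the pairing and the period, although the SAP keeps both for its other continuous endpoints. The direction is certain given positive within-subject correlation: the test is conservative and can miss moderate differences.

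The size is an illustration that rests on the assumed log-normal times, spread, correlation and 111 pairs. Fewer pairs may be available for symptom relief, because "Only subjects with baseline score at least 2 or more (for ANS, AAS, or ATS) will be evaluable for this analysis".

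The primary non-inferiority decision is unaffected. Preparation time is affected little in practice: the protocol describes current kits as a nine-step process and G-Pen as needing no reconstitution, so a large difference is expected and either test should find it. The missing censoring variable is a lesser matter of code clarity.

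**What to change.** 1. In SAP 6.6.4 and Appendix 2, make the treatment comparison account for subject and period. One option is a Cox model with treatment and period, a sandwich variance clustered on subject (PHREG with COVS(AGGREGATE) and an ID statement) and a stated tie method such as Efron for the 5-minute grid, reporting the hazard ratio with its 95% CI. It also uses subjects with only one evaluable period. Its downside is an error slightly above nominal, about 5–6% at this size.
2. For preparation time, a mixed model on log time with treatment, period and random subject would serve.
3. Keep the Kaplan-Meier curves and label the unpaired log-rank descriptive.
4. As a lesser point, add a censoring variable to the sample code, so that subjects without the event are not counted as events. This includes those recorded at their last assessment under SAP 5.3.6.2.3.
5. The sponsor should reconcile how subjects given glucose for non-response (Protocol 7.3) are handled in these analyses with the rule that censors data after an intervention (Protocol 10.2.1.2, SAP 4.1).

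Cost: SAP wording and a few lines of code. No new data are needed.
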